2.1.2 Analysis sets

The screened set (SCR) consists of all participants who signed the informed consent. The screened set includes only uniquely screened participants, i.e., in the case of re-screened participants, only the chronologically last screened data is counted. Screening phase disposition will be based on the SCR.

The randomized set (RND) consists of all participants who signed the informed consent and were randomized, including misrandomizations.

The full analysis set (FAS) will include all participants who were transplanted and randomized, excluding mis-randomized participants. Mis-randomized participants are defined as cases where IRT contacts were made by the Investigator/qualified site staff either prematurely or inappropriately to confirmation of the participant's final randomization eligibility and treatment was not administered to the participant. Following the intention-to-treat (ITT) principle, participants will be analyzed according to their treatment assignment at randomization. Participant demographics, baseline characteristics, efficacy and renal function measured by GFR will be performed on the FAS.

The safety set (SAF) consists of all participants in FAS who received at least one dose of study drug (i.e., at least one dose of TAC after randomization in the Control arm and at least one dose of CFZ533 in the CFZ533 arms). Participants will be analyzed according to the treatment they actually received. All safety analyses, including renal function parameters other than GFR, will be performed on the SAF using on-treatment (between start and end of treatment defined in Section 2.1.1) data unless otherwise specified.

The PK analysis set (PKS) will include all participants with at least one available valid (i.e., not flagged for exclusion) PK concentration measurement, who received any study drug and with no protocol deviations that impact on PK data, e.g. if a dose was taken more than 7 days after the planned date.

The total screened participants and each analysis population above will be summarized in terms of the frequencies and percentages. Listings of randomized participants and of the participants excluded from analysis sets will be provided.

Rules for exclusion from analysis sets is in Table 5-9.

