Mis-randomized participants	Mis-randomized participants are those who were not qualified for randomization and who did not take study treatment, but have been inadvertently randomized into the study
Other treatment	Treatment that may be needed/allowed during the conduct of the study (i.e., concomitant or rescue therapy)
Participant	A trial participant (can be a healthy volunteer or a patient)
Participant number	A unique number assigned to each participant upon signing the informed consent. This number is the definitive, unique identifier for the participant and should be used to identify the participant throughout the study for all data collected, sample labels, etc.
Period	The subdivisions of the trial design (e.g., Screening, Treatment, Follow-up) which are described in the Protocol. Periods define the study phases and will be used in clinical trial database setup and eventually in analysis

Glossary of terms

Personal data	Participant information collected by the Investigator that is coded and transferred to Novartis for the purpose of the clinical trial. This data includes participant identifier information, study information and biological samples
Premature participant withdrawal	Point/time when the participant exits from the study prior to the planned completion of all study drug administration and/or assessments; at this time all study drug administration is discontinued and no further assessments are planned
Randomization number	A unique identifier assigned to each randomized participant
Run-in Failure	A participant who is screened but not randomized/treated after the run-in period (where run-in period requires adjustment to participant's intervention or other treatment)
Screen Failure	A participant who did not meet one or more criteria that were required for participation in the study
Source Data/Document	Source data refers to the initial record, document, or primary location from where data comes. The data source can be a database, a dataset, a spreadsheet or even hard-coded data, such as paper or eSource
Start of the clinical trial	The start of the clinical trial is defined as the signature of the informed consent by the first participant
Study treatment	Any drug or combination of drugs or intervention administered to the study participants as part of the required study procedures; includes investigational drug(s), control(s) or background therapy

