6.7.2.2 Tacrolimus administration

All participants need to be on a treatment regimen comprising TAC, CS and MMF at the time of randomization.

Initiating TAC before transplantation is permitted.

Initiation of tacrolimus post-transplantation

Tacrolimus will be administered as capsules orally twice daily. Tacrolimus should be initiated as soon as possible after transplantation and TAC blood trough levels should be targeted and adjusted between 5-15 ng/mL (i.e., all participants should be treated exactly according to the same local treatment protocol). The use of intravenous tacrolimus in the immediate post-operative period is permitted.

Arm 1

Participants randomized to the Control Arm 1 will continue to receive TAC, in combination with MMF and corticosteroids until EOS. TAC will be administered as p.o. capsules/tablets b.i.d. and blood trough levels will be managed according to the local approved label.

Novartis	Confidential	Page 68 of 136
Amended Clinical Trial Protocol (Version No.	04 clean)	Protocol No. CCFZ533A2202

Every effort should be made to keep the participants within target trough levels as per local label. TAC dose adjustments will be based on local laboratory trough level results.

In the event of TAC intolerance, dose reduction of TAC may be necessary. If this occurs, the change in TAC regimen and the TAC dosing should be recorded on the appropriate CRF.

Arms 2 and 3

For the CFZ533 (Arms 2 and 3) participants; TAC dose will be progressively decreased up to Day 21 as described thereafter. At randomization, on the day of the first CFZ533 loading dose (30 mg/kg IV), the TAC dose will be reduced to achieve a TAC blood trough level of 5-8 ng/mL.

The TAC dose will be further decreased by Day 15 to reach a TAC blood trough level below 5 ng/mL. By Day 22, TAC must be completely weaned-off. If, at any time post Day 22 and for any reason, TAC is not completely withdrawn and co-administration with the randomized study treatment is ongoing, an immediate discussion will be needed between the Sponsor and the Investigator whether to keep the participant on randomized treatment; this will be assessed on a case-by-case basis.

In case a participant temporarily cannot take oral TAC (e.g., in case of a surgical intervention), TAC intravenous administration is allowed as per local practice. TAC granules for oral suspension are also allowed to be used for participants who cannot swallow tablets.

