12.1 Analysis sets

The screened set (SCR) consists of all participants who signed the informed consent.

The full analysis set (FAS) will include all participants who are transplanted and randomized, excluding mis-randomized participants. Mis-randomized participants are defined as cases where IRT contacts were made by the Investigator/qualified site staff either prematurely or inappropriately for confirmation of subject's final randomization eligibility and treatment was

Novartis	Confidential	Page 110 of 136
Amended Clinical Trial Protocol (Version No.	04 clean)	Protocol No. CCFZ533A2202

not administered to the participant. Following the intention-to-treat (ITT) principle, participants will be analyzed according to their treatment assignment at randomization.

The safety set (SAF) consists of all participants who received at least one dose of study drug (i.e., at least one dose of TAC after randomization in the control arm and at least one dose of CFZ533 in the CFZ533 arms). Participants will be analyzed according to the treatment they actually received.

All safety analyses will be performed on the SAF. The safety will be presented separately for the treatment and follow-up periods.

The PK analysis set will include all participants with at least one available valid (i.e., not flagged for exclusion) PK concentration measurement, who received any study drug and with no protocol deviations that impact on PK data.

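### The FAS exclusion of mis-randomised participants depends on dosing after open-label randomisation, so it can remove undosed CFZ533 participants but hardly any controls

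*SAP*

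**What the plan says.** **The exclusion.** Protocol 12.1 begins the definition this way: "Mis-randomized participants are defined as cases where IRT contacts were made by the Investigator/qualified site staff either prematurely or inappropriately". Both it and SAP 2.1.2 then add a second condition, so that the contact must have preceded or lacked confirmation of "final randomization eligibility and treatment was not administered to the participant". The Protocol glossary also joins two conditions: "Mis-randomized participants are those who were not qualified for randomization and who did not take study treatment". The same FAS paragraph invokes the intention-to-treat principle.

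**What counts as a dose.** The FAS rule does not define treatment. The safety-set paragraph of SAP 2.1.2 does so by arm: "at least one dose of TAC after randomization in the Control arm and at least one dose of CFZ533 in the CFZ533 arms". The Protocol glossary is wider; its study treatment "includes investigational drug(s), control(s) or background therapy".

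**Treatment around randomisation.** Protocol 6.7.2.2 states: "All participants need to be on a treatment regimen comprising TAC, CS and MMF at the time of randomization". For control it continues: "Participants randomized to the Control Arm 1 will continue to receive TAC, in combination with MMF and corticosteroids until EOS". In Arms 2 and 3, CFZ533 begins with a separate infusion on the day of randomisation (Protocol 6.7.2.1). Protocol 6.4 describes the trial as open-label to participants, site staff and the sponsor team.

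**Where the set is used.** The primary analysis and the eGFR analysis use the FAS (SAP 2.1.2, 2.4, 2.5.1). SAP 2.1.2 defines a randomised set (RND) that keeps mis-randomised participants, but assigns it no efficacy analysis. SAP 2.4.4 plans no sensitivity analysis. SAP Table 5-9 also excludes from the FAS on three protocol-deviation codes, in any arm, without giving their meaning.

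**The concern.** Whether a person randomised in error leaves the FAS turns on an event after randomisation whose probability differs by arm. A control participant is on twice-daily TAC and meets the dosing condition almost automatically. A CFZ533 participant does not meet it until a separate infusion is given by staff who know the assignment. If an error is noticed in between, the infusion can be withheld and the participant leaves the FAS; the equivalent control participant stays.

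Some criteria checked at randomisation bear on outcome: earlier rejection, vascular thrombosis, graft function, systemic infection (Protocol 5.1 and 5.2). If people who fail them have more composite failures, keeping them in control and dropping the undosed ones from CFZ533 raises the control rate relative to CFZ533. That makes the 15-point success rule easier to meet without any treatment effect.

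**Working it through.** **1. The rule by arm, using the safety-set meaning of a dose**

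| Ineligible participant randomised to | Event after randomisation | In the FAS? |
|---|---|---|
| Control | Next TAC dose taken (the default) | Yes |
| CFZ533 | First infusion given | Yes |
| CFZ533 | First infusion withheld | No |

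Only the last row leaves under this rule. On the glossary meaning, which includes background therapy, nobody in any arm counts as untreated and the exclusion is empty. So the rule is either arm-dependent or without effect.

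**2. The plan's own figure**

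Inputs (SAP 3.2, same as Protocol 12.7): 48 per CFZ533 arm, 32 controls, Beta(1/3, 1/3) priors, success if the posterior probability of a difference below 0.15 exceeds 0.8. Enumerating both binomials exactly at true rates 0.11 and 0.103 gives 0.904, as in Table 3-2. All 15 cells of that table agree within 0.001.

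**3. Size of the shift (assumed inputs)**

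The documents give neither the number of mis-randomised participants nor their risk. Assume:

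- m: share mis-randomised, equal in all arms, 2-10%
- q: failure risk of a mis-randomised control, 10.3% to 40%
- p_C = 0.103: failure rate of the other controls (the table's grid value for the expected 10%)
- the same true arm difference in mis-randomised and other participants
- f: fraction of mis-randomised CFZ533 participants whose first infusion is withheld

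Compared with keeping everyone, dropping the undosed from CFZ533 shifts the difference by

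shift = -m × f × (1 - m) × (q - p_C) / (1 - m × f),

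which at f = 1 is -m × (q - p_C).

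| m | q | f | Shift in failure-rate difference |
|---|---|---|---|
| any | 0.103 | any | 0 |
| 0.02 | 0.20 | 1 | -0.02 × 0.097 = -0.2 points |
| 0.05 | 0.20 | 1 | -0.05 × 0.097 = -0.5 points |
| 0.05 | 0.40 | 0.5 | -0.025 × 0.95 × 0.297 / 0.975 = -0.7 points |
| 0.05 | 0.40 | 1 | -0.05 × 0.297 = -1.5 points |
| 0.10 | 0.40 | 1 | -0.10 × 0.297 = -3.0 points |

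**4. Effect on the success rule, f = 1**

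For m = 0.05 and q = 0.40 the control rate is 0.95 × 0.103 + 0.05 × 0.40 = 0.118. With rates of 0.11 and 0.103 in the other participants, the CFZ533 rate is 0.125 if all are kept and 0.11 on 46 participants if the undosed are dropped.

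| Rates in other participants (CFZ533, control) | m, q | All kept | Undosed CFZ533 dropped |
|---|---|---|---|
| 0.11, 0.103 | 0.05, 0.40 | 0.882 | 0.934 |
| 0.253, 0.103 (true difference 0.15) | 0.05, 0.40 | 0.216 | 0.268 |
| 0.253, 0.103 | 0.10, 0.40 | 0.214 | 0.322 |

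Part of the movement in the first row is discreteness: at equal risk (q = 0.103), going from 48 to 46 participants alone moves 0.904 to 0.915. In the second row that effect is negligible (0.217 to 0.215). At a 2% share the success probability moves by about 2 to 3 points or less.

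**5. Which analyses this describes**

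Steps 3 and 4 use the binomial design model, which is the Protocol's primary analysis. SAP 2.4.2 replaces it with a Poisson model on on-treatment time that ends at treatment discontinuation. There a never-dosed CFZ533 participant adds almost no time even if kept in the FAS. SAP 2.1.1 does apply control-arm dates to CFZ533 participants who stop before their first dose, but SAP 2.4.2 does not repeat this. The Kaplan-Meier analysis (SAP 2.4.5) censors at last contact, and the main eGFR analysis does not stop at treatment discontinuation, so both can use data from undosed participants.

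**The case against.** Several counter-arguments stand and limit the point.

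- **The window is short.** Sites contact the randomisation system only after confirming eligibility (Protocol 6.3.2), and the first infusion is on the same day. A reader might infer that ineligible participants in general leave the CFZ533 arms. The documents do not support that: those who were dosed remain.
- **Control is not immune to exclusion.** The Table 5-9 deviation codes apply in every arm. Their meaning is not given, so they cannot be counted as an offset, but they rule out saying that every ineligible control stays.
- **The asymmetry rests on one reading of an undefined word.** It needs the safety-set meaning of a dose. That is the nearest definition; the alternative makes the exclusion empty, which is also a reason to repair the wording.
- **Worse prognosis is assumed.** A premature contact may be procedural, and some randomisation criteria, such as body weight or donor SARS-CoV-2 history, need not predict failure. At equal risk the shift is zero.
- **eGFR.** A reader might infer that eGFR is also biased towards CFZ533. The endpoint is change from randomisation, adjusted for the randomisation value, so a low starting eGFR does not fix the direction.
- **Some transparency is planned.** SAP 2.1.2 summarises the analysis sets and lists excluded participants.
- **The trial has ended early.** An abbreviated report follows termination for unfavourable risk-benefit (SAP 1). This lowers the stakes but does not make the exclusion neutral.

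**Conclusion.** The point holds in limited form. On the safety-set meaning of a dose, the FAS exclusion is a post-randomisation, arm-dependent step in an open-label trial, at odds with the intention-to-treat principle claimed beside it. Its direction favours CFZ533 on the composite endpoint if the excluded participants have a worse prognosis.

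The size is unknown. The range of 0 to about 3 points rests wholly on the assumed shares and risks, and its upper end needs a 10% share, a 40% risk and every mis-randomised CFZ533 participant caught before dosing. Nothing in the documents shows that any mis-randomisation occurred or that any infusion was withheld because of the arm.

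A reader might also infer that the SAP's primary result is materially biased and that restoring these participants would correct it. That is not supported: on-treatment follow-up leaves them with almost no weight. The gain lies mainly in the Kaplan-Meier and eGFR analyses and in the Protocol's binomial analysis. This is an inexpensive improvement, not a fatal flaw.

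**What to change.** In SAP 2.1.2, SAP Table 5-9 and Protocol 12.1, define the FAS as all randomised and transplanted participants, analysed as randomised, and delete the exclusion that depends on no treatment having been given. If the present FAS is kept, at least repeat the primary, Kaplan-Meier and eGFR analyses on the transplanted participants of the RND set. In either case report mis-randomised participants by arm and reason, and state what the three Table 5-9 codes mean.

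The cost is a wording change and one re-derived flag. The downside is that a few undosed CFZ533 participants with little follow-up may enter the FAS: Protocol 8.1.1 treats people who never start treatment as early terminators, although Protocol 8 expects all randomised participants to be followed to Month 24. Under the Protocol's binomial rule (12.4.3), those lost to follow-up would count as failures, which works against CFZ533.

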2.4 Analysis of the primary objective

The primary objective is to evaluate the rate of composite efficacy failure (BPAR, graft loss, or death) with CFZ533 600 mg and 300 mg Q2W maintenance regimen compared to TAC Control at Month 12 post-transplantation. Analysis will be on the FAS.

The analysis of the primary objective has been modified due to the early termination of the study.

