5.6 Rule of exclusion criteria of analysis sets

Table 5-9_displays the criteria for exclusions from analysis sets.

Table 5-9	Participant Classification		
Analysis Set	PD ID that cause participants to be excluded	Non-PD criteria that cause participants to be excluded	
SCR	INCL01	Not having informed consent;	
		Not having screening epoch disposition page	
FAS	INC03, OTH03, OTH10	Not randomized; Not transplanted;	
		Mis-randomized	
SAF	NA	No study drug taken	

Analysis Set	PD ID that cause participants to be excluded	Non-PD criteria that cause participants to be excluded
РК	NA	No study drug taken; PD with relevant impact on PK; no valid PK concentration measurement

6 Reference

Garwood, F (1936). Fiducial limits for the Poisson distribution. Biometrika, 46; 441–453.

Sahai H, Khurshid Anwer (1993). Confidence intervals for the mean of a poisson distribution: a review. Biom J, 35 (7); 857-867

Ulm K (1990). A simple method to calculate the confidence interval of a standard mortality ratio. American Journal of Epidemiology, 131(2); 373-375

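### SAP 2.1.2 nests the safety set in the FAS, against Protocol 12.1 and the SAP's own Table 5-9, so a dosed participant with one of three undefined deviation codes would leave the safety tables

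*SAP*

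**What the plan says.** - **Protocol 12.1, SAF:** "The safety set (SAF) consists of all participants who received at least one dose of study drug". For control this means at least one TAC dose after randomisation; for the CFZ533 arms, at least one CFZ533 dose. FAS membership is not required.
- **SAP 2.1.2, SAF:** "The safety set (SAF) consists of all participants in FAS who received at least one dose of study drug". The dosing condition is the same, with the restriction to the FAS added.
- **SAP 2.1.2, FAS:** "The full analysis set (FAS) will include all participants who were transplanted and randomized, excluding mis-randomized participants". Mis-randomisation is defined as a premature or inappropriate IRT contact where "treatment was not administered to the participant". Protocol 12.1 is the same in substance.
- **SAP 5.6, Table 5-9, FAS row:** the deviation column lists "INC03, OTH03, OTH10". A separate column gives the non-deviation reasons: not randomised, not transplanted, mis-randomised.
- **SAP 5.6, Table 5-9, SAF row:** the deviation column reads NA and the only other reason is "No study drug taken".
- **Status of the table:** SAP 2.1.2 makes it operative: "Rules for exclusion from analysis sets is in Table 5-9".
- **Use of the sets:** for the primary objective, SAP 2.4 says "Analysis will be on the FAS". The eGFR and new-onset diabetes analyses also use the FAS. SAP 2.7 runs the safety analyses on the SAF unless otherwise specified.
- **Declared changes:** SAP Section 4, on changes to protocol-specified analyses, reads not applicable.

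**The concern.** A safety set should hold everyone exposed to study drug, which is how the protocol defines it. Making it a subset of the FAS means that any exclusion written for efficacy also removes adverse events. That would be harmless if the FAS lost only untreated people, as its text implies. Table 5-9, however, adds three deviation codes to the FAS exclusions, and deviations do occur in treated participants: Protocol 6.2.2 foresees a participant found on a non-protocol immunosuppressant after randomisation who stays on study treatment with the deviation noted.

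Two things are at stake. The first is complete safety reporting in a trial that SAP Section 1 says was terminated because risk-benefit was no longer favourable. The second is agreement between the FAS as built and the ITT principle stated for it. In addition, 2.1.2 and Table 5-9 give different safety sets, so two programmers could follow the SAP and reach different denominators.

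**Working it through.** This is a check of definitions; no planned figure is in dispute. Take one participant who was randomised, transplanted, received at least one dose of CFZ533 (or of TAC after randomisation in control) and carries one of INC03, OTH03 or OTH10.

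| Rule | In FAS? | In SAF? |
|---|---|---|
| Protocol 12.1 | Yes: transplanted, randomised, not mis-randomised | Yes: dosed |
| SAP 2.1.2, FAS sentence alone | Yes: only the mis-randomised are excluded | Yes: in FAS and dosed |
| SAP Table 5-9, read row by row | No: code listed | Yes: deviation column NA, drug taken |
| SAP 2.1.2 with the Table 5-9 FAS row | No | No: the SAF must lie within the FAS |

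Three results follow.

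1. On the SAF, the last two rows disagree. The SAP conflicts with itself, and the reading that follows the 2.1.2 wording also conflicts with the protocol.
2. On the FAS, Table 5-9 is wider than the 2.1.2 sentence. The mis-randomised exclusion requires that treatment was not administered, and the three codes carry no such limit.
3. Section 4 declares neither difference.

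**Size per affected participant.** The planned sizes are 48 per CFZ533 arm and 32 in control (SAP 3.2 and 3.3). One participant is 1/48 = 2.1% or 1/32 = 3.1% of an arm. The number affected is not given, so the total effect runs from zero upwards and cannot be fixed from the documents.

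**Illustration for the FAS only, with assumed counts.** This uses the SAP 2.4.2 rule: Poisson counts, Gamma(0.001, 0.001) prior on each rate, θ = 1 − exp(−λ), success if P(θ_CFZ533 − θ_control < 0.15 | data) > 0.8. Assume one person-year each, 48 and 32 participants, and 3 control failures. With 10 CFZ533 failures in 48 person-years the posterior probability is 0.771 (not successful). Removing one failing CFZ533 participant leaves 9 in 47 and gives 0.829 (successful). With 2 to 5 control failures and mean follow-up of 0.8 or 1.0 year, each combination has a CFZ533 count at which one such removal crosses 0.8. The protocol's binomial rule with Beta(1/3, 1/3) priors behaves alike: with 3/32 control failures, 9/48 gives 0.789 and 8/47 gives 0.853. These counts were chosen at the boundary. They show that one exclusion could matter, not that one occurred.

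**The case against.** The strongest reply is that the codes are undefined here and may touch nobody who was dosed. In the SCR row of Table 5-9, code INCL01 sits beside lack of informed consent, and inclusion criterion 1 is consent. By that pattern INC03 could be inclusion criterion 3 (primary liver transplant from a deceased donor), partly restating the not-transplanted reason beside it. This is plausible but is itself inference, and it says nothing about OTH03 or OTH10. It stands as a limit on the size of the point. It does not remove the conflict over the SAF.

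A second reply is that the FAS condition may have a purpose. All participants are already on TAC at randomisation (Protocol 6.7.2.2), and TAC is supplied locally as standard of care (Protocol 6.1.1). A mis-randomised control patient who simply continued local TAC could meet the wording of at least one TAC dose after randomisation; a mis-randomised CFZ533 patient who was never given CFZ533 could not. The restriction keeps such patients out of the control safety set. This stands, and the fix has to preserve it.

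Third, SAP 2.1.2 promises a listing of participants excluded from analysis sets, and SAP 2.1 says the plan may differ from the protocol after early termination. Both are true. But a listing does not put events back into rates, and the general remark neither names nor justifies a narrower safety set.

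A reader might go further and infer that the three codes are the only route by which the nesting can matter. The documents do not support that: someone dosed without having been randomised would also be lost, and the control patient just described is a further case. Nor does the text show that any adverse event is actually being dropped, or that a treatment comparison is biased; that would need the code definitions and the counts.

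**Conclusion.** The point holds as a conflict between definitions with a possible, unquantified consequence. SAP 2.1.2 narrows the protocol's safety set and disagrees with the SAF row of Table 5-9. Through the FAS row, it would remove from the safety analyses any dosed participant carrying one of the three codes. The same codes would remove that participant from the FAS, which the FAS text does not provide for.

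The conclusion assumes that Table 5-9 is applied as 2.1.2 directs and that the codes can apply to dosed participants, which the documents neither state nor rule out. The number affected may be zero, in which case no result changes. Loss from every output does not follow either: the PK set is not nested in the FAS. The SAF part is secure on the text alone. The FAS part is less so, because the meaning of the codes is unknown. The correction should be made before the sets are programmed or, if that is done, checked against them.

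**What to change.** 1. **SAF (SAP 2.1.2).** Delete the words *in FAS*, so that the SAF is every participant who received at least one dose of study drug, as in Protocol 12.1 and the SAF row of Table 5-9. State that mis-randomised participants, to whom study treatment was not administered, stay out, so that continued local TAC alone does not bring them into the control arm.
2. **FAS (Table 5-9).** Define INC03, OTH03 and OTH10 in the SAP. Limit them to participants never dosed, or remove them, so that the table agrees with the FAS sentence in 2.1.2.
3. **SAP Section 4.** Replace the not-applicable entry with any departure from Protocol 12.1 that remains.
4. **Report the count.** In the exclusion listing already planned, flag any dosed participant carrying one of the codes, by arm.

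The cost is a few lines of SAP text and, if the sets are already built, one re-derivation of the population flags. No new data are needed.
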